The hyperinsulinemic-euglycemic clamp technique (17) was first adapted for use in children and adolescents by [name] (my primary mentor) and his colleagues in a study that demonstrated that the hormonal changes of puberty induced a physiologic state of insulin resistance in healthy lean adolescents compared to healthy lean preadolescents and young adults (2). In follow-up studies, these investigators used the stepped hyperinsulinemic-euglycemic clamp in combination with stable isotope infusions to demonstrate that the insulin resistance of normal puberty was related to impairments in insulin's ability to stimulate peripheral glucose uptake; whereas, insulin's ability to suppress hepatic glucose production did not appear to be adversely affected (11). [name] (my secondary mentor) has used similar techniques to describe, in depth, the metabolic consequences of obesity in non-diabetic children over the past 20 years (12-20), including indirect calorimetry to measure rates of glucose and fat oxidation. Nevertheless, the effect of obesity on hepatic and peripheral insulin sensitivity in adolescents with T1D during puberty has not been established; this is the gap in knowledge that AIM 1 of this study is intended to fill. This Aim is particularly significant, as adolescents with T1D have the poorest glycemic control and may gain the most benefit from pharmacologic intervention to improve insulin sensitivity, promote weight loss, and reduce cardiovascular complications.

Based on recent work establishing branched chain amino acids (BCAAs) and α -hydroxybutyrate as markers of peripheral and hepatic insulin resistance in obese youth without T1D (21,22), I will work [REDACTED] to use targeted nuclear magnetic resonance (NMR) spectroscopy to assess these relationships in lean and obese adolescents with T1D. Validation of these recently identified biomarkers reflecting peripheral or hepatic insulin resistance in adolescents in our study cohorts will help identify patients who may particularly benefit from targeted early interventions.

Fatty liver disease in obese adolescents with T1D

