Investigators have demonstrated that two to four weeks of treatment with SGLT2i results in a shift from glucose oxidation to fat oxidation (35,36) in adults with T2D. Additionally, a small study has shown that SGLT2i therapy lowers ALT in adults with T2D and ultrasound diagnosed hepatic steatosis, unrelated to weight loss (40).

4. **Research Plan:** Summarize the study design and research procedures using non-technical language that can be readily understood by someone outside the discipline. Be sure to distinguish between standard of care vs. research procedures when applicable, and include any flowcharts of visits specifying their individual times and lengths. Describe the setting in which the research will take place.

Overview: This is a cross-sectional study of 72 adolescents and 36 young adults with T1D who will undergo comprehensive metabolic evaluation. The study consists of 2 visits which will take place over approximately 30 days. The study aims to enroll 36 adolescents with T1D and overweight/obesity, 36 lean adolescents with T1D, and 36 young adults with T1D. To characterize the impact of adiposity on metabolism during puberty, adolescents will undergo the euglycemic hyperinsulinemic clamp study with tracer enhancement and DEXA scan on the Hospital Research Unit, and abdominal MRI in the Magnetic Resonance Resource Center. The lean young adults with T1D will provide a control group to reflect prepubertal youth with T1D, and will undergo the euglycemic hyperinsulinemic clamp study with tracer enhancement and DEXA scan.

Subjects: This study will enroll 36 obese/overweight and 36 lean adolescents (Tanner stage 2-5) with T1D. A comparison control group of 36 lean young adults with T1D will also be enrolled, since they will be unaffected by the adverse metabolic effects of puberty or obesity.

Study visits: Enrollment and both study visits will take place over approximately 30 days. All participants will undergo screening to evaluate study eligibility through the elicitation of a medical history and physical examination and laboratory tests.

Enrollment: Screening will be conducted by invitation to potentially eligible subjects during which written informed consent will be obtained prior to conducting any study related procedures. After informed consent has been obtained and documented, subjects will undergo a history and directed physical exam, anthropometric measures, and hemoglobin A1c. A HbA1c done in the past 30 days may be used.

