[figure not shown]
Visit 1: A hyperinsulinemic-euglycemic clamp will be conducted as a gold standard assessment of insulin sensitivity, with infusion of a stable

Hyperinsulinemic Euglycemic Clamp

glucose isotope in order to distinguish hepatic from peripheral insulin action.

Baseline glucose and glycerol turnover	Hepatic sensitivity to insulin (low dose infusion)	Peripheral sensitivity to insulin (high dose infusion)
Hyperinsulinemic euglycemic clamp		

Clamp studies will be carried out following methods utilized in Dr.

[name]'s lab ^{3,5}, as described briefly below. Participants will be admitted to the Hospital Research Unit (HRU) the evening prior to the clamp procedures for transition to IV insulin and stabilization of blood glucose with target of 90-100. On admission urine will be dipped for ketones, and if present, ketones will be managed as per routine clinical practice. If present, ketones will be monitored throughout treatment and the study will be delayed or cancelled pending resolution of ketosis. All participants will be advised to limit exercise in the 3 days prior to study to limit acute effects of recent exercise on insulin sensitivity. Females in the study who have reached menarche and have regular menses will be asked to keep a menstrual diary so that we can plan to study them during the follicular phase of the menstrual cycle (more insulin sensitive phase).

Baseline assessments will include liver function tests, lipids, sex steroids, IGF-1 (measure of growth hormone secretion), isoleucine, leucine, valine, and α -hydroxybutyrate.

- *Non-radioactive, Stable Isotope Tracer Infusions* will be employed to assess rates of glucose and lipid metabolism at the end of the 120 min baseline equilibration period and during the two stepped IV insulin infusion periods. From -120 to 0 min, 4.5 mg/kg of 6,6-²H₂-glucose (99% enriched; Cambridge Isotope Laboratories, Andover MA) will be followed by a continuous infusion at 0.03 mg/kg/min⁷. ²H₅-glycerol will be infused at 1.6 μ mol/kg followed by a constant infusion of 0.11 μ mol/kg/min⁷ to assess glycerol turnover. During the 120 min basal turnover period, a variable rate insulin infusion will be utilized to maintain plasma glucose between 90-110 mg/dL.

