- i. the types of future research to be conducted using the materials, specifying if immortalization of cell lines, whole exome or genome sequencing, genome wide association studies, or animal studies are planned *Write here*
- ii. the plan for the collection of material or the conditions under which material will be received *Write here*
- iii. the types of information about the donor/individual contributors that will be entered into a database *Write here*
- iv. the methods to uphold confidentiality *Write here*

B. What are the conditions or procedures for sharing of materials and/or distributing for future research projects? *Write here*

C. Is widespread sharing of materials planned? *Write here*

D. When and under what conditions will materials be stripped of all identifiers? *Write here*

E. Can donor-subjects withdraw their materials at any time, and/or withdraw the identifiers that connect them to their materials? *Write here*

- i. How will requests to withdraw materials be handled (e.g., material no longer identified: that is, anonymized) or material destroyed? *Write here*

F. Describe the provisions for protection of participant privacy *Write here*

G. Describe the methods for the security of storage and sharing of materials *Write here*

6. **Subject Population:** Provide a detailed description of the types of human subjects who will be recruited into this study.

This study aims to enroll 36 obese/overweight adolescents and 36 lean adolescents with T1D. A comparison control group of 36 lean young adults with T1D matched for gender and HbA1c will also be enrolled, since they will be unaffected by the adverse metabolic effects of puberty or obesity.

7. **Subject classification:** Check off all classifications of subjects that will be specifically recruited for enrollment in the research project. Will subjects who may require additional safeguards or other considerations be enrolled in the study? If so, identify the population of subjects requiring special safeguards and provide a justification for their involvement.

 Children	 Healthy	 Fetal material, placenta, or dead fetus
 Non-English Speaking	 Prisoners	 Economically disadvantaged persons
 Decisionally Impaired	 Employees	 Pregnant women and/or fetuses

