Associations of these assessments with measures of insulin sensitivity will be explored for all groups. Unadjusted differences in the group means of primary and secondary outcomes of interest between lean and obese adolescent subjects, as well as between lean young adults and lean adolescent subjects, will be examined using the Student's t-test or the Mann-Whitney U test for variables with Gaussian and not normal distributions respectively. The impact of group, gender, sex hormones, pubertal stage, and growth factors on the outcome measures will also be explored using multivariable linear regression modeling. For the primary adjusted analysis, we will treat group as a categorical variable, and conduct two post-hoc pair-wise comparisons of means at alpha of 0.025. For the secondary adjusted analysis, we will also treat our three groups of subjects as an ordinal variable, whereby the lowest level will be given to the obese adolescents, followed by the lean adolescents, and then lean young adults. The latter approach will allow us to obtain a linear increase in the mean glucose disposal rate across the three groups, thus allowing us to use an alpha level of 0.05. The outcome variable will be normalized, if needed, using the natural log function.

Visit 2: Abdominal MRI: Sample Size: Based on mean hepatic lipid content in healthy overweight/obese and lean children ¹⁰, groups sizes of 36 lean and 36 obese adolescents will achieve >99% power at alpha of 0.05 to detect a difference between group means of 3.5% (SD=2) and 1.5% (SD=0.5). Even if a few subjects decline participation in this Aim, we will still have 90% power at alpha of 0.05 to detect the projected effect size using with a minimum of 12 subjects per group.

Data Analysis Approach:

The Proton Density Fat Fraction (PDFF) , a biomarker for hepatic steatosis, will be calculated from the liver images obtained liver PDFF parametric maps ⁹. A PDFF value above 5.5% is indicative of fatty liver ¹¹.

• Statistical Analysis: Descriptive statistics (mean, standard deviation, count, and percent) will be used to characterize the groups. Continuous variables will be compared between the lean and obese adolescents using either the Student's t-test or the Mann-Whitney U test. Categorical variables will be compared with the Chi-square test or the Fisher's Exact test. Associations of the following assessments with hepatic fat fraction will be explored through Spearman Correlation.

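### Read naturally, the primary adjusted model conditions the lean-adolescent versus young-adult comparison on puberty itself, so its coefficient is not the contrast that arm was recruited to give

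*Combined protocol and SAP*

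**What the plan says.** The young adults are there to supply a state without puberty. Item 4 (Research Plan, Overview) says: "The lean young adults with T1D will provide a control group to reflect prepubertal youth with T1D". Item 6 (Subject Population) gives the reason: "since they will be unaffected by the adverse metabolic effects of puberty or obesity". The Background rests on earlier clamp work showing that "the hormonal changes of puberty induced a physiologic state of insulin resistance in healthy lean adolescents".

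Item 13 (Visit 1, Statistical Analysis) describes three layers:
- A test of "Unadjusted differences in the group means of primary and secondary outcomes of interest", for obese versus lean adolescents and for lean young adults versus lean adolescents.
- A multivariable linear regression: "The impact of group, gender, sex hormones, pubertal stage, and growth factors on the outcome measures will also be explored".
- Two named adjusted analyses. "For the primary adjusted analysis, we will treat group as a categorical variable, and conduct two post-hoc pair-wise comparisons of means", at alpha 0.025. "For the secondary adjusted analysis, we will also treat our three groups of subjects as an ordinal variable", at alpha 0.05.

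Neither adjusted analysis has a covariate list of its own. Item 8 sets a Tanner range (2 to 5) for adolescents only, and nothing says how pubertal stage is coded for young adults.

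**The concern.** The regressors listed beside group are the only ones the plan names before it turns to the adjusted analyses, so they are what a programmer would enter. Gender is harmless. Pubertal stage, sex hormones and growth factors are either puberty itself or its hormonal pathway. Holding them fixed while comparing pubertal adolescents with post-pubertal adults removes from the coefficient the thing the comparison was set up to show.

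This comparison has its own alpha and its own sample-size statement. The adjusted version is called primary, carries the same 0.025, and is not ranked against the unadjusted test. The two versions answer different questions and may disagree in either direction. A reader could take the adjusted figure as the size of the puberty effect.

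**Working it through.** **Inputs from item 13:** 36 per group; SD 3; lean adolescent mean 13.6 and obese mean 11.5 mg/kg lean body mass/min; alpha 0.025 per pair; a detectable increase of 15-18% in young adults; an expected increase of about 30%.

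**Assumed, because the documents do not give them:** two-sided tests; nine adolescents at each of Tanner 2, 3, 4 and 5 in both adolescent groups; adults coded 5; the same stage effects in both adolescent groups; residual SD 3 in every model.

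**1. The plan's own figure.** Without stage, SE = 3 × √(2/36) = 0.707. The difference detectable with 80% power is (2.241 + 0.842) × 0.707 = 2.18, and 2.18/13.6 = 16.0% (16.3% with the t distribution). This agrees with the stated 15-18%.

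**2. What adjustment does.** Adjusted contrast = unadjusted contrast − Σ (covariate coefficient × adult-minus-adolescent difference in that covariate). With categorical stage and adults coded 5, this is adults versus Tanner-5 adolescents.

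**3. Precision.** The variance without stage is 9 × 2/36 = 0.5.
- Linear stage: the adolescent mean is 3.5, so the gap to adults is 1.5. The within-group sum of squares is 72 × 1.25 = 90. Variance = 0.5 + 1.5² × 9/90 = 0.725; SE = 0.851; inflation 1.45.
- Categorical stage: variance = 0.5 + 9 × (1/18 − 1/72) = 0.875; SE = 0.935; inflation 1.75.

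The added covariates would have to explain 1 − 1/1.45 = 31% (linear) or 1 − 1/1.75 = 43% (categorical) of the residual variance to offset this. With other assumed mixes over stages 2 to 5, the break-even share is 15% or 20% (3/6/9/18) and 50% or 73% (12/12/9/3).

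**4. Power (noncentral t, two-sided 0.025), same true difference at every stage.**

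| True difference | No stage | Linear | Categorical |
|---|---|---|---|
| 18% (2.45), even mix | 88% | 73% | 63% |
| 30% (4.08), even mix | >99% | 99% | 98% |
| 30% (4.08), mix 12/12/9/3 | >99% | 96% | 76% |

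**5. Estimate under assumed stage patterns.** Each set of deficits relative to adults averages 2.45 over stages 2 to 5.
- Uniform: unchanged, 2.45.
- Declining (4, 3, 2, 0.8): categorical 0.80. Linear: slope 1.06 per stage, so 2.45 − 1.5 × 1.06 = 0.86.
- Rising (0.8, 2, 3, 4): categorical 4.00; linear 2.45 + 1.5 × 1.06 = 4.04.

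I give no power for the last two patterns. The stage effects there have variance 1.41, about 16% of 9, so a residual SD of 3 both with and without stage cannot hold exactly.

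**6. Ordinal model.** Without stage, the slope per level is (2.1 + 2.45)/2 = 2.27. With stage it is 2.24-2.25 (uniform), 1.56-1.58 (declining) or 2.86-2.94 (rising).

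**7. Adults in their own stage category.** That indicator is identical to the young-adult group indicator. The design has rank 6 for 7 columns, and the comparison cannot be estimated.

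**8. Obese versus lean adolescents.** With equal Tanner mixes the SE stays at 0.707. If the obese group were 3/6/9/18 against an even lean group, linear stage would give √(0.5 + 0.667² × 9/80) = 0.742. Here stage is an ordinary covariate.

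The same identity in step 2 applies to sex hormones and growth factors, but the documents give nothing from which to quantify them.

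**The case against.** The strongest reply is that the plan never says all the listed variables enter the primary adjusted model. It says their impact will be explored, which fits exploratory modelling of several determinants, and the next sentence fixes only the coding of group and the alpha. That is correct, and it is why the point is conditional. It does not remove the problem. If the list does not feed the adjusted analyses, those analyses have no stated covariates at all, and a comparison labelled primary is left open.

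Second, the intended contrast is not lost. The unadjusted pairwise test is planned for this pair, and the sample size rests on unadjusted means. The title and aims concern adiposity, and the obese versus lean comparison does not have this problem. All of that stands and limits the harm.

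Third, the unadjusted contrast is not a clean puberty effect either. Ages differ (12-16 versus 18-24 years), and so does the definition of lean (BMI below the 75th percentile versus 18.5-24.9 kg/m²). This also stands: the fix restores the plan's intended contrast, not a pure effect of puberty.

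Fourth, the sizes depend on an assumed Tanner mix, adult coding and stage effects. They do, and they are illustrative. The change in what is estimated does not depend on the particular mix chosen.

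**Conclusion.** The point holds in conditional form and should be fixed. On the natural reading, the adjusted young-adult comparison and the ordinal model estimate a residual difference at fixed pubertal status. That is not the pubertal versus non-pubertal contrast for which the arm was recruited. The estimate is less precise unless the added covariates explain enough residual variance, and it cannot be computed under one plausible coding of adult stage. For the ordinal model the problem is meaning rather than power.

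A reader might infer more than the documents support:
- That adjustment must shrink or abolish the puberty effect. The direction depends on how the deficit varies by stage, which is not given.
- That the comparison becomes underpowered. At the expected 30% it keeps 98-99% power with an even mix. The lower figures come from the 18% difference or an unfavourable mix.
- That the study cannot show the intended contrast. The unadjusted test does.

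Confidence is medium, because the covariate set of the adjusted models is inferred from adjoining sentences.

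**What to change.** In item 13:
- Name the covariates of each adjusted comparison.
- Leave pubertal stage, sex hormones and growth factors out of the primary adjusted lean-adolescent versus young-adult comparison and out of the ordinal secondary model. Gender may stay.
- Report models that contain those variables separately, labelled as exploratory mechanism analyses, and state how adult Tanner stage is coded in them.
- Pubertal stage may stay in the obese versus lean adolescent comparison.
- State whether the unadjusted or the adjusted result takes precedence.

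The cost is analysis-plan wording only, with no new data or visits. The downside is two covariate sets to maintain and explain instead of one.

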- i. How will adverse events and unanticipated problems involving risks to subjects or others be reported, reviewed and managed? *Write here*
- ii. What provisions are in place for management of interim results? *Write here*
- iii. What will the multi-site process be for protocol modifications? *Write here*

13. **Statistical Considerations:** Describe the statistical analyses that support the study design.

Visit 1 Euglycemic Hyperinsulinemic Clamp: Sample Size: Prior work evaluating insulin sensitivity in youth with T1D is limited in consistency in reporting insulin-mediated glucose disposal. Thus, for sample size calculation, glucose infusion rate will be utilized as this calculation is more consistent across studies and can provide a good estimate of glucose disposal. A clinically meaningful difference would be at least 20% reduction in mean glucose disposal rate from lean to obese. In addition, we expect T1D lean young adults to have the highest mean glucose infusion rate, reflecting the anticipated response in T1D children not affected by hormonal changes of puberty (2). Therefore, we propose to compare the three means in a sequential manner: obese vs. lean adolescents with T1D, and lean adolescents with T1D vs. lean young adults with T1D, thus reducing the alpha level of 0.05 by $\frac{1}{2}$.

Using published literature (43,44), we will need 36 lean and 36 obese/overweight pubertal adolescents with T1D, to have 80% at alpha of 0.025, to detect a difference between group means of 13.6 (SD=3) and 11.5 mg/kg lean body mass/min (SD=3); and 36 lean young adults to detect a minimum percent increase in glucose infusion rate in the range of 15-18% from that of lean pubertal adolescents with T1D - for the respective sequential group comparisons. Of note, the literature suggests that the actual increase for the latter is around 30% ², therefore, we should be sufficiently powered.

An interim analysis will be conducted when we recruit 15 subjects in each group. If significant differences will be observed at that time, we will reconsider the sample size.

Data Analysis Approach: The departmental biostatistician [name], will guide [name] in analysis.

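### The secondary ordinal model assumes a linear increase across the three groups and cannot show one; the plan should limit what its slope may conclude

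*Combined protocol and SAP*

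**What the plan says.** The text is in Section I, item 13 (Statistical Considerations), Visit 1, under Statistical Analysis. The multivariable model is introduced this way: "The impact of group, gender, sex hormones, pubertal stage, and growth factors on the outcome measures will also be explored". Two versions of the group term follow.

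- Primary adjusted analysis: group is categorical, and the investigators will "conduct two post-hoc pair-wise comparisons of means at alpha of 0.025".
- Secondary adjusted analysis: "For the secondary adjusted analysis, we will also treat our three groups of subjects as an ordinal variable", with obese adolescents lowest, lean adolescents next and lean young adults highest. The stated gain is "The latter approach will allow us to obtain a linear increase in the mean glucose disposal rate across the three groups". From this gain the plan derives the significance level of the test: "thus allowing us to use an alpha level of 0.05".

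The plan gives the order but no scores, and no rule for what a significant slope may be said to show.

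The Visit 1 sample-size text sets out the expectations. Lean and obese adolescents have means of 13.6 and 11.5 mg/kg lean body mass/min (SD 3 each). For young adults, "we expect T1D lean young adults to have the highest mean glucose infusion rate"; the detectable increase over lean adolescents is 15-18%, and "the literature suggests that the actual increase for the latter is around 30" per cent. No SD is given for young adults. Section I, item 6 explains the choice of young adults as controls: "since they will be unaffected by the adverse metabolic effects of puberty or obesity".

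**The concern.** A model with one slope for ordered scores imposes equal steps between groups. The slope can be positive and significant when only one step exists, so it does not deliver the property that the plan attributes to it.

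This matters because the first aim is the effect of adiposity, and only the obese-versus-lean adolescent contrast isolates that. The outer groups differ in both puberty and obesity, so the slope cannot say which step produced it. The plan expects young adults to be clearly higher. If the adiposity difference turns out small or absent, a significant slope is still likely at the planned SD, and the plan's wording would describe it as an increase across all three groups.

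**Working it through.** **Plan's own figures.** The documents give no power or error rate for the ordinal model, so there is none to reproduce. The nearest figure is 80% power at alpha 0.025 for 13.6 versus 11.5 with 36 per group. Two-sided, I get 76.7% (normal) or 75.0% (t). Nothing below rests on that difference.

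**Inputs.** From the plan: n = 36 per group, lean mean 13.6, obese mean 11.5, adolescent SD 3, young adults +15, +18 or +30% (2.04, 2.448 or 4.08 units). Assumed: scores 1, 2, 3; two-sided tests; the same SD in young adults (SD 4 also shown); infusion-rate planning values used for disposal rate.

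**What the slope is.** With equal group sizes, slope = Σ(x − 2)·mean / Σ(x − 2)² = (young adults − obese adolescents) / 2. Lean adolescents have weight zero.

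**Is linearity expected?** The obese-to-lean step is 13.6 − 11.5 = 2.1. The lean-to-adult step is 2.04 to 2.45 at 15-18%, which is close to linear, but 4.08 at 30%, which is not.

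**Obese equal to lean (both 13.6), unadjusted.** The slope test is nearly a two-group test of the outer groups. The standard error of their difference is 3 × √(2/36) = 0.7071.

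- +15%: 2.04 / 0.7071 = 2.885; 2.885 − 1.96 = 0.925; power about 82%.
- +18%: 2.448 / 0.7071 = 3.462; 3.462 − 1.96 = 1.502; power about 93%.
- +30%: 4.08 / 0.7071 = 5.770; 5.770 − 1.96 = 3.810; power over 99.9%.

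Simulating the regression itself (200,000 trials per scenario) gives 81, 92 and over 99.9%.

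**The same, adjusted.** The covariates were sex, balanced within group, and Tanner stage: 5 in all adults; in adolescents either uniform over 2-5 or 10/20/30/40% in stages 2/3/4/5. They were given no effect of their own. Sex hormones and growth factors were not modelled. The mean slope weights become −0.54 to −0.57 (obese), +0.08 to +0.13 (lean) and +0.43 to +0.46 (adults), so lean adolescents still count for little.

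| Obese = lean; slope significant | +15% | +18% | +30% |
|---|---|---|---|
| Unadjusted, SD 3 | 81% | 92% | >99.9% |
| Adjusted, SD 3 | 55-65% | 69-80% | 98-99.6% |
| Unadjusted, SD 4 | 57% | 72% | 99% |
| Adjusted, SD 4 | 34-42% | 46-56% | 87-94% |

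The obese-versus-lean contrast at 0.025 is significant in about 2.5% throughout.

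**Small adiposity effect (obese 5% below lean), adjusted, SD 3.** Slope significant in 85-91, 92-96 and over 99.8%; obese-versus-lean contrast in about 10%.

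**Plan's means, adjusted, SD 3.** Slope significant in at least 99.8%. In about 25% of trials it is significant while the obese-versus-lean contrast misses 0.025. The true order is increasing here, so the slope is right about order.

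**The case against.** The strongest reply is that the plan already ranks these analyses. The categorical model is primary and the ordinal model secondary; group means, an overall three-group test and both adjacent contrasts are also planned. A reader would see any conflict. That stands, and it makes the point minor.

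A reader might infer that 0.05 for the slope is an error, or that it inflates the trial's error rate. The documents do not support this. Alpha is halved because there are two comparisons; the slope is one test, so no split is needed within that model. With three equal means it rejects at 5%. Only if it were read as confirmatory beside the two 0.025 tests would the chance of any false positive reach about 8.5%, and nothing in the plan makes it confirmatory.

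A reader might also infer that the investigators will report the slope as an obesity effect. The plan does not say so. What it does say is that the slope yields an increase across the three groups, and that is the statement to correct.

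Finally, the high rates are conditional. They need young adults well above lean adolescents and an SD near 3. At SD 4 the adjusted slope is significant in less than half of trials at +15% and in about half at +18%. If pubertal stage, hormones or growth factors explain part of the adult increase, the adjusted rates fall further. All of this limits the size of the problem; it does not give the slope the ability to show linearity.

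**Conclusion.** The point holds as a minor one. The plan credits the secondary slope with showing a linear increase, which a single slope assumes. If obese and lean adolescents do not differ, whether the slope is usually significant depends on the adult increase and the SD. It is so at every increase the plan names with SD 3, adjusted or not. At SD 4 in the adjusted model it is so clearly only at +30%. The adjusted figures rest on assumed covariate distributions without covariate effects, and no young-adult SD is stated.

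The primary contrasts are untouched. The slope misleads only when one of the two steps is small or absent.

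**What to change.** In the Visit 1 Statistical Analysis text, replace the sentence that contains "The latter approach will allow us to obtain a linear increase in the mean glucose disposal rate across the three groups" and ends with the alpha remark by:

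> The ordinal model (scores 1, 2, 3) estimates an assumed linear trend and is supportive (nominal two-sided 0.05); its slope and 95% CI will be reported beside both adjacent contrasts from the primary categorical model. A significant slope alone will not be described as an increase across all three groups or as an effect of obesity. An obesity effect rests on the obese-versus-lean contrast. An increase across all three groups will be claimed only if both primary contrasts are positive and significant at their 0.025 level.

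No new data are needed, and the ordinal model and primary tests stay as they are. With obese equal to lean, the rule falsely claims an ordered increase in at most about 1.25% of trials, because the obese-versus-lean contrast must be significant in the positive direction (0.025 / 2).

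The cost is that an ordered increase becomes harder to claim. Under the plan's means at SD 3, with adults +15, +18 or +30%, the claim succeeds in about 51, 64 and 76% unadjusted, or 36-41, 50-56 and 74-75% adjusted. The slope is significant nearly always.

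Requiring only 0.05 per contrast would succeed more often (66, 77 and 84% unadjusted). However, in about 8-15% of trials (the differences between those figures and the 0.025 ones) it would claim an ordered increase while at least one primary contrast fails its own level. Tying the claim to 0.025 avoids that conflict.
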